#### **2.5.6 Supportive analyses**

CCI

#### **2.5.7 Supplementary analyses**

CCI

### **2.6 Analysis supporting secondary objectives**

The secondary objectives of the study are provided in [Table 1-1](#).

#### **2.6.1 Secondary endpoint(s)**

The secondary endpoints are:

- Assessment of safety based on vital signs, physical examination, ECGs, laboratory assessments, and collection of AEs assessed from baseline until the end of the study visit
- AKI stages 1, 2 and 3 as defined by modified AKI Network (AKIN) criteria
- Anti-drug antibodies (ADA) against TIN816
- Occurrence of major adverse kidney event at Day 90 (MAKE90) as a composite of individual components
- Occurrence of MAKE30 as a composite of individual components

- Occurrence of individual components of the MAKE criteria at Days 30 or 90

## **2.6.2 Statistical hypothesis, model, and method of analysis**

The statistical evaluation of all secondary efficacy data will be descriptive. Hypothesis testing will not be performed.

Assessment of safety is defined in [Section 2.7](#) and ADA analysis is defined in [Section 2.9](#).

### **2.6.2.1 Acute Kidney Injury based on AKIN criteria**

CCI

CCI

#### **2.6.2.2 Major Adverse Kidney Events**

All MAKE30 and MAKE90 related analyses will be performed based on the safety set.

MAKE30 and MAKE90 are defined as a composite of:

1. death through day 30/90,
2. initiation of renal replacement therapy through day 30/90, or
3.  $\geq 25\%$  reduction in calculated eGFRcre from baseline to 30/90 days after surgery.

The proportion of participants per MAKE30 outcome (Yes, No, Not Available) and MAKE90 outcome (Yes, No, Not Available) will be summarized by treatment. MAKE30 and MAKE90 outcome will also be listed by participant and treatment.

There will be three categories: Yes for the participants meeting at least one of the above-mentioned criteria, No for the participants not meeting any of the criteria, and Not Available for the participants who do not have sufficient data to conclude MAKE30 or MAKE90.

Similarly, the proportion of participants by each of the individual components of MAKE90 and MAKE30 mentioned above will be summarized by treatment. The individual components will also be listed by participant and treatment.

#### **2.6.3 Handling of intercurrent events**

Not applicable.

#### **2.6.4 Handling of missing values not related to intercurrent event**

Refer [Appendix 5.1](#) for imputation rules, and [Appendix 5.3](#) for laboratory parameters derivation. No other imputation will be done.

## **2.6.5 Sensitivity analyses**

Not Applicable.

## **2.6.6 Supplementary analyses**

Not Applicable.

## **2.7 Safety analyses**

For all safety analyses, the safety analysis set will be used. All listings and tables will be presented by the treatment group.

Safety summaries (tables, figures) will show events that started on Study Day 1 (including data collected for events prior to start of treatment, i.e. intra-surgery, as well as post start of treatment, i.e., post-surgery), and events that started on Study Day 2 and later. Baseline data, which may have been reported on Study Day 1 prior to surgery or on Day of Screening, will also be summarized where appropriate (e.g., change from baseline summaries), utilizing Day 1 data whenever available for both days. In addition, a separate summary for deaths including on treatment and post treatment deaths will be provided. In particular, summary tables for adverse events (AEs) will summarize only on-treatment events, with a start date during the on-treatment period i.e., from Day 1 (treatment-emergent AEs).

The on-treatment period lasts from the date of first administration of study treatment until EOS (i.e., D90 or date of last study visit in the event of early study discontinuation).

### **2.7.1 Adverse events (AEs)**

All information obtained on adverse events will be listed by treatment group and participants.

All AE summary tables will be created for two periods: AEs which occurred only on Day 1, vs. AEs that occurred on and after Day 2 and end by Day 90 (EOS).

The treatment emergent adverse events (TEAEs) are defined as the events started from Day 1 or events present prior to start of Day 1 but increased in severity based on preferred term. The number and percentage of participants with TEAEs will be summarized in the following ways for both periods (defined above) and overall (from Day 1 to EOS):

- by treatment, primary system organ class and preferred term
- by treatment, primary system organ class, preferred term and maximum severity.

Separate summaries will be provided for study medication related adverse events, death, serious adverse events, and other significant adverse events leading to discontinuation, dose interrupted/withdrawn, and adverse events by severity class by period, treatment, primary system organ class and preferred term.

A participant with multiple adverse events within a primary system organ class is only counted once towards the total of the primary system organ class.

A 'Total' column will be shown for all AEs related summaries.

A similar separate summary will be created for non-serious adverse events accounting for >5% of all recorded adverse events by system organ class and preferred term.

All adverse events and serious adverse events will be listed by study day, treatment group and participant.

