9.4.1 Safety endpoints

For all safety analyses, the safety set will be used. All listings and tables will be presented by treatment group.

Safety summaries (tables, figures) include only data from the on-treatment period with the exception of baseline data which will also be summarized where appropriate (e.g. change from baseline summaries). In addition, a separate summary for death including on treatment and post treatment deaths will be provided. In particular, summary tables for adverse events (AEs) will summarize only on-treatment events, with a start date during the on-treatment period (treatment-emergent AEs).

The on-treatment period lasts from the date of first administration of study treatment to 90 days (EOS) after the date of actual administration of any study treatment.

Adverse events

All information obtained on adverse events will be displayed by treatment group and participant.

The number (and percentage) of participants with treatment emergent adverse events (events started after the first dose of study medication or events present prior to start of blinded treatment but increased in severity based on preferred term) will be summarized in the following ways:

- by treatment, primary system organ class and preferred term.
- by treatment, primary system organ class, preferred term and maximum severity.

Separate summaries will be provided for study medication related adverse events, death, serious adverse events, and other significant adverse events leading to discontinuation.

The number (and proportion) of participants with adverse events of special interest will be summarized by treatment group.

A participant with multiple adverse events within a primary system organ class is only counted once towards the total of the primary system organ class.

Vital signs

All vital signs data will be summarized by treatment group and visit/time and if ranges are available, abnormalities (and relevant orthostatic changes) will be flagged. Summary statistics will be provided by treatment group and visit/time for raw and change from baseline.

12-lead ECG

PR, QRS, QT, QTcF, and RR intervals will be obtained from 12-lead ECGs for each participant during the study. **CCI**

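### The SAP counts intra-operative events that began before the infusion as treatment-emergent, which dilutes post-infusion differences in adverse events

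*SAP*

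**What the plan says.** Order of events: participants are randomized at the start of surgery, and the infusion is given only once the main surgery is complete (SAP 1.1; Protocol 4.1). SAP 2.1.1 defines Day 1 as the calendar date of dosing, which is also the day of surgery.

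SAP definition (2.7.1): "The treatment emergent adverse events (TEAEs) are defined as the events started from Day 1", or as events already present before Day 1 that then became more severe. SAP 2.7 describes the Day 1 summaries as "including data collected for events prior to start of treatment, i.e. intra-surgery, as well as post start of treatment, i.e., post-surgery".

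Protocol definition (9.4.1): "events started after the first dose of study medication or events present prior to start of blinded treatment but increased in severity". The same protocol section also equates treatment-emergent events with those whose start date lies in the on-treatment period, and sets that period by date: "The on-treatment period lasts from the date of first administration of study treatment to 90 days (EOS" (quotation cut before the bracket closes). SAP 2.7 does likewise: "The on-treatment period lasts from the date of first administration of study treatment until EOS".

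Tables (SAP 2.7.1): numbers and percentages of participants by system organ class and preferred term, and by maximum severity. They are given for Day 1, for Day 2 onward, and overall.

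**The concern.** Anaesthetic, bypass and surgical events on Day 1 that start before the infusion cannot be caused by the drug, yet the SAP labels them treatment-emergent. The reference point for worsening moves as well. A pre-existing condition that worsens during surgery, before any drug is given, becomes treatment-emergent.

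This is the first trial of TIN816 in patients, and safety is a secondary objective. Protocol 6.2.3 requires close observation for at least an hour after the infusion, and Protocol 6.8.3 provides for hypersensitivity reactions and major bleeding. Intra-operative hypotension or bleeding may share a preferred term with such events. Because a participant counts once per term, someone with a pre-infusion event adds nothing further to incidence if the term recurs after infusion. The maximum-severity table may likewise show a grade reached before exposure.

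**Working it through.** The documents give no figure on this point, so there is none to reproduce. The check compares the definitions and then sizes the consequence under stated assumptions.

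**1. Definitions side by side**

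| | Onset rule | Worsening rule |
|---|---|---|
| Protocol 9.4.1, definition | after first dose | present before blinded treatment, then worse |
| Protocol 9.4.1, on-treatment period | start date on or after the dosing date | not stated |
| SAP 2.7.1 | from Day 1 | present before Day 1, then worse |

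The SAP onset rule agrees with the protocol's date-based sentence and conflicts with its explicit definition. SAP 2.7 settles how the SAP is to be read, because it names intra-surgery events before treatment as included.

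**2. Which events change status.** Events that start on Day 1 before the infusion are added, as are earlier conditions that worsen on Day 1 before the infusion. No event with onset after the infusion is lost.

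**3. Which tables are affected.** The Day 1 and overall tables are affected. The Day 2 onward table is not, because a pre-infusion Day 1 onset cannot fall in it.

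**4. Dilution.** For one preferred term, let q be the incidence before infusion, and p0 and p1 the incidence after infusion on placebo and TIN816. Assume that q is equal in the arms and that pre- and post-infusion occurrence are independent. Then:

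- tabulated incidence = q + (1 − q)p
- tabulated difference = (1 − q)(p1 − p0)

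Example at q = 20%: 0.20 + 0.80 × 0.15 = 0.32 and 0.20 + 0.80 × 0.30 = 0.44. The difference is 0.80 × 15 = 12 points and the ratio is 0.44/0.32 = 1.38, against a post-infusion ratio of 2.00.

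All rates below are assumptions.

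| q | 15% vs 30% becomes | Ratio | 5% vs 20% becomes | Ratio | Difference (points) |
|---|---|---|---|---|---|
| 0 | 15 vs 30 | 2.00 | 5 vs 20 | 4.00 | 15 |
| 1% | 15.85 vs 30.7 | 1.94 | 5.95 vs 20.8 | 3.50 | 14.85 |
| 10% | 23.5 vs 37 | 1.57 | 14.5 vs 28 | 1.93 | 13.5 |
| 20% | 32 vs 44 | 1.38 | 24 vs 36 | 1.50 | 12 |
| 40% | 49 vs 58 | 1.18 | 43 vs 52 | 1.21 | 9 |
| 60% | 66 vs 72 | 1.09 | 62 vs 68 | 1.10 | 6 |

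The loss of difference is trivial for terms rarely recorded during surgery and large for common ones. The ratio is more sensitive than the difference when the placebo rate after infusion is itself small.

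**5. If q is not equal.** With no drug effect (p0 = p1 = p), the table would show a difference of (1 − p)(q1 − q0), in either direction. Randomization protects concurrently randomized arms. It protects less well here, because the two dose groups enrolled under successive protocol versions and SAP 2.1 compares each with placebo pooled across versions.

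I have not converted the dilution into power, because the readable text plans no test of adverse events.

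**The case against.** A reader might infer that the SAP simply contradicts the protocol. The documents do not support that in full. Protocol 9.4.1 contains two rules that do not agree, and the SAP follows the date-based one. SAP section 4, on changes to protocol-specified analyses, is redacted, so an undeclared departure cannot be shown either. What stands is that the protocol's explicit definition says after the first dose, and that declaring a departure would not stop pre-exposure events being labelled treatment-emergent.

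A reader might also infer that acute drug effects are hidden. That is too strong:

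- No post-infusion onset is dropped.
- Day 1 is tabulated apart from Day 2 onward.
- There are separate summaries of drug-related events, serious events, and events leading to discontinuation or dose interruption.
- All events are listed by study day.
- SAP 1.1 says the phases of Day 1 will be distinguished where possible.
- The section on events of special interest (SAP 2.7.1.1) is redacted and may contain a finer split.
- Protocol 2.3.3 says hypersensitivity may be immediate or delayed by weeks, so not all the risk falls on Day 1.

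These points reduce the harm to dilution in some tables. They do not remove it, because no readable adverse-event table is split at infusion start.

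A further objection is practical. Protocol 8.6.1 asks for start and end dates of adverse events and does not mention times. SAP Table 5-1 has a rule for missing start times, which implies a time field, but not that it is well filled. This stands as a limit on what the correction can achieve.

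**Conclusion.** The definition is wrong as written and should be fixed. SAP 2.7 and 2.7.1 place events that precede exposure in the treatment-emergent incidence and maximum-severity tables, against the explicit definition in Protocol 9.4.1. That protocol section needs reconciling with itself.

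The consequence is dilution by the factor (1 − q) in the Day 1 and overall tables. It is negligible for terms with low q, and takes 15 points down to 12 at q = 20% and to 9 at q = 40%. These sizes rest on assumed event rates, equal q across arms, and independence of pre- and post-infusion occurrence. None of these comes from the documents. The trial is non-confirmatory and its adverse-event summaries are descriptive, so the point concerns how clearly a signal can be seen and not the validity of a test.

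**What to change.** - Define a treatment-emergent event as one with onset, or worsening, at or after the start date and time of the infusion. Use the same wording in SAP 2.7, SAP 2.7.1 and Protocol 9.4.1, and align the on-treatment period with it.
- Show Day 1 events that began before the infusion in a separate column or table, labelled as not treatment-emergent.
- Class Day 1 events without a recorded start time as post-infusion, which the 23:59 rule in SAP Table 5-1 already implies, unless a recorded end time precedes the infusion. Do not use imputed end times for this exception. SAP Table 5-2 sets a missing end time to 00:00, which would wrongly place a Day 1 ending before the infusion.
- Report how many Day 1 events lack a recorded start time.

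Optional additions are a separate window from infusion start to 24 hours, and change from the scheduled pre-dose (0H) value for vital signs and limited haematology.

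The cost is SAP wording and programming, plus aligned protocol text. Infusion start and end times are already recorded in the eCRF (Protocol 6.4). The drawback is that the gain depends on how completely Day 1 onset times are recorded. If most are missing, the default rule largely reproduces the present tables.

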#### **2.7.1.1 Adverse events of special interest / grouping of AEs**

CCI

#### **2.7.2 Deaths**

Incidence of death will be summarized by treatment groups and will be listed by treatment groups and participant.

#### **2.7.3 Laboratory data**

Some laboratory parameters were collected from both, local and central labs. In case of duplicate information, local lab results will be preferred over central labs.

All laboratory data (absolute, change from baseline and ratio to baseline) will be summarized by treatment group, and visit/time.

All laboratory data parameters (hematology, clinical chemistry, lipid panel, renal chemistry, urine chemistry, urine microscopy/sediment, urine dipstick, CCI hepatitis testing, and liver event/follow-up testing) will additionally be listed by treatment group, participant and visit/time, and if local normal ranges are available, then abnormalities will be flagged in the listing.

Below notable severe drug induced liver injury (including Hy's law) will be summarized using count and percentage by treatment group:

- ALT or AST > 5x ULN
- ALT or AST >3xULN
- ALT or AST >3x ULN and TBL >2x ULN
- ALT or AST >3xULN and INR >1.5xULN)

- ALP >2xULNALT or AST >3x ULN and TBL >2x ULN and ALP <2xULN (Hy's law cases).

A spaghetti plot and box plot will be created for all laboratory parameters over time by treatment group, with a line indicating the treatment group mean.

CCI

Another spaghetti plot will be generated for the liver monitoring parameters from liver monitoring visits and local/central lab, over study day, by treatment. In case of more than one record is available at a particular day, the highest value will be considered. The AKI stage 2 and stage 3 participants will be highlighted in the plot.

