10.5.1 Liver event and laboratory trigger definitions & follow-up requirements

Table 10-2 Liver event and laboratory trigger definitions

	Definition/ threshold
Liver laboratory triggers:	ALT or AST > 5 × ULN
If ALT, AST and total bilirubin normal at baseline:	
ALP > 2 × ULN (in the absence of known bone pathology)
 
Total bilirubin > 3 × ULN (in the absence of known Gilbert syndrome)
 
ALT or AST > 3 × ULN and INR > 1.5
 
Potential Hy's Law cases (defined as ALT or AST > 3 × ULN and Total bilirubin > 2 × ULN [mainly conjugated fraction] without notable increase in ALP to > 2 × ULN)
 
Any clinical event of jaundice (or equivalent term)
 
ALT or AST > 3 × ULN accompanied by (general) malaise, fatigue, abdominal pain, nausea, or vomiting, or rash with eosinophilia
 
Any adverse event potentially indicative of a liver toxicity

If ALT or AST abnormal at baseline:	ALT or AST > 3x baseline AND > 5x ULN

Table 10-3 Follow up requirements for liver laboratory triggers - ALT, AST, TBL

ALT	TBL	Liver Symptoms	Action
ALT increase without bilirubin increase:			
• No change to study treatment• Measure ALT, AST, ALP, GGT, TBIL, INR, albumin and CK in 48-72 hours.• Follow-up for symptoms.• Initiate close monitoring and workup for competing etiologies.
If normal at baseline: ALT > 5 x ULN for more than two weeks OR ALT > 8 x ULN	Normal For participants with Gilbert's syndrome: No change in baseline TBL	None	
If elevated at baseline: ALT > 3 x baseline AND > 5x ULN for more than two weeks OR ALT ≥ 5x baseline AND ≥ 8x ULN			
ALT increase with bilirubin increase:			
If normal at baseline: ALT > 3 x ULN	TBL > 2 x ULN (or INR > 1.5) For participants with Gilbert's syndrome: Doubling of direct bilirubin	None	
If elevated at baseline: ALT > 2 x baseline AND >3x ULN			
If normal at baseline: ALT > 3 x ULN	Normal or elevated*	Severe fatigue, nausea, vomiting, right upper quadrant pain*	
If elevated at baseline: ALT > 2 x baseline AND > 3x ULN			
* This situation suggests liver injury based on (i) elevation of ALT, and (ii) the presence of symptoms of liver injury. Even if bilirubin is normal, the presence of liver symptoms indicates potentially severe liver injury.			

Table 10-4 Follow up requirements for liver laboratory triggers - Isolated Hyperbilirubinemia

Criteria	Actions required	Follow-up monitoring
Total Bilirubin (isolated)		

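### The SAP 2.7.3 liver table uses INR above 1.5×ULN where protocol Tables 10-2 and 10-3 use INR above 1.5, so its INR row can omit participants who met the protocol trigger

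*SAP*

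**What the plan says.** **INR.** The list in SAP 2.7.3 that opens with "Below notable severe drug induced liver injury" gives counts and percentages by treatment group for fixed multiples of the upper limit of normal (ULN). Its combined transaminase and INR row reads "ALT or AST >3xULN and INR >1.5xULN". Protocol section 10.5.1 puts no ULN multiplier on INR. Table 10-2 pairs ALT or AST above three times the limit with a plain INR ("ULN and INR > 1.5"), and Table 10-3 allows INR as an alternative to raised bilirubin ("TBL > 2 x ULN (or INR > 1.5").

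**Baseline.** The liver list itself carries no baseline condition, but other sections bear on it:
- Protocol 9.4.1 limits safety summaries to data from the on-treatment period, apart from baseline data.
- SAP 2.7 has a start rule, "Safety summaries (tables, figures) will show events that started on Study Day 1" (or later), and treats pre-surgery values as baseline: "Baseline data, which may have been reported on Study Day 1 prior to surgery or on Day of Screening".
- SAP 2.1.1 defines the safety baseline as the last non-missing value before surgery.
- Protocol 8.6.3 describes a potential Hy's Law case through treatment-emergent transaminase elevations.

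**The concern.** A participant can meet the liver trigger that obliges the site to act and yet be absent from the row of the safety table that looks designed to report that combination. The SAP cut-off also depends on each laboratory's reference limit. Protocol 8.4.5 sends safety samples to local laboratories, so the same INR can count at one site and not at another. Rows of this kind hold very few participants and are read case by case, so one omission is visible.

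A smaller question concerns the heading. An elevation that was there before surgery and persists after dosing still meets the fixed multiple, and is then counted under a drug-induced label although nothing changed.

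**Working it through.** **INR inputs.** SAP multiplier 1.5 (SAP 2.7.3) and protocol cut-off 1.5 (Tables 10-2 and 10-3). The documents give no ULN for INR, so 1.0 to 1.3 is assumed.

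SAP cut-off as a plain INR = 1.5 × ULN. Band of protocol triggers missed = 1.5 × ULN − 1.5.

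| Assumed INR ULN | SAP cut-off | Protocol cut-off | Band missed |
|---|---|---|---|
| 1.0 | 1.5 × 1.0 = 1.50 | 1.5 | 0 |
| 1.1 | 1.5 × 1.1 = 1.65 | 1.5 | 0.15 |
| 1.2 | 1.5 × 1.2 = 1.80 | 1.5 | 0.30 |
| 1.3 | 1.5 × 1.3 = 1.95 | 1.5 | 0.45 |

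Take a participant with normal baseline values who develops ALT above 3×ULN with INR 1.6. The protocol trigger is met, since 1.6 > 1.5. The SAP row counts the participant if the limit is 1.0 (1.6 > 1.50) but not if it is 1.1 (1.6 < 1.65). With INR 1.7 the participant is counted at a limit of 1.1 (1.7 > 1.65) and not at 1.2 (1.7 < 1.80), which shows the dependence on the laboratory.

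One omitted participant is 1/20 = 5.0%, 1/40 = 2.5% or 1/60 = 1.7% of an arm of 20, 40 or 60. These arm sizes are assumed, because the allocation is redacted.

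**Persisting elevation, illustrative values in multiples of ULN.**
- AST 4 before surgery and 4 after dosing: the post-dose value is counted in the >3×ULN row. It is not newly met, because 4 > 3 already held at baseline.
- ALT 2 before and 5.5 after: counted in the >3× and >5× rows and newly met in both, because 2 is below each cut-off.

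The existing rows do not separate an unchanged value from a new rise. A newly-met count does.

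**The case against.** **On INR.** Tables 10-2 and 10-3 govern what the site does, and a summary table may use its own cut-off. The width of the gap rests on an assumed reference limit. A participant with ALT above 3×ULN and INR 1.6 is not lost to reporting: that participant stays in the >3×ULN row and in the laboratory and liver-event listings. All of this is fair and keeps the point minor. It does not explain why the row departs from the protocol's own INR value, and no reason is readable.

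**On baseline.** A reader might infer that the table will tally pre-surgery samples as drug-induced injury, because the QT categories in SAP 2.7.4.1 are limited to post-baseline visits and the liver categories are not. The documents do not support that. The on-treatment restriction in protocol 9.4.1 speaks of data, so it reaches laboratory values, and SAP 2.7 classes a pre-surgery Day 1 value as baseline. The missing phrase is a lack of detail. Marked entry elevations are also unlikely. Exclusion 26 targets liver disease or injury shown by abnormal liver tests, and exclusion 28 names ALT, GGT and ALP above 3×ULN, though not AST. What remains is the post-dose value of an elevation that persists.

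A reader might also infer that the SAP must copy the Table 10-2 rule headed "If ALT or AST abnormal at baseline", namely "ALT or AST > 3x baseline AND > 5x ULN", or its Table 10-3 counterpart. As site-action triggers these need not be reproduced. Change-from-baseline and ratio-to-baseline summaries, flagged listings and individual plots are already planned in SAP 2.7.3.

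**Conclusion.** The INR mismatch stands as a minor inconsistency between the SAP and both protocol tables. At any laboratory with an INR limit above 1.0 the SAP row is the stricter of the two and can omit participants who met the protocol trigger. The band missed is 0.15 to 0.45 INR units wide for an assumed limit of 1.1 to 1.3. It would be wrong to conclude that liver cases go unreported.

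The baseline matter is secondary. A persisting pre-surgery elevation can be counted under a drug-induced heading, which sits awkwardly with the treatment-emergent wording of protocol 8.6.3.

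Both effects stay within one descriptive safety table, and the number of participants involved is unknown and may be zero. The conclusion rests on the readable text: part of SAP 2.7.3 and all of SAP section 4 are redacted and could hold a reason for the INR cut-off or a baseline rule.

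**What to change.** **Main change.** In SAP 2.7.3, set the combined row to INR >1.5, or show INR >1.5 and INR >1.5×ULN side by side. This is a one-line edit. The lower cut-off may add counts that reflect anticoagulant effect and not liver injury, which is a reason to prefer showing both; the placebo column helps in reading them.

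**Optional addition.** Keep every existing row and add beside it the number of participants newly meeting the criterion after dosing, meaning that it was not met at the safety baseline of SAP 2.1.1. This costs a few small counts and a programming condition per row, and no signal is removed. Two limits deserve a footnote. Rises caused by surgery will also count as new. And a combined row, such as Hy's law, can become newly met through bilirubin alone while the transaminase is unchanged, so those cases should still be read from the listing. Flags for the baseline multiples in Tables 10-2 and 10-3 are not needed.
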